9.3. Variables

The study will collect all relevant data including patient demographics (e.g., age and sex), comorbidities, prescription medications, vaccinations, procedures, and laboratory tests prior to initiating abrocitinib and while on treatment to address the study objectives. Abrocitinib and concomitant medications and vaccinations will be identified using ATC codes. Diagnoses will be recorded using diagnostic codes. Performance of laboratory tests, available from Denmark, will be identified using Nomenclature, Properties and Units (NPU) codes. Surgeries will be defined using country-specific procedure/surgery codes. Age (date of birth) and sex will be used as reported in the databases. The average daily dose of abrocitinib will be estimated using a combination of information available per country: strength of the prescription dispensed, packet size, World Health Organization (WHO) defined daily dose and duration of therapy (time between prescriptions/dispensings). Availability of specific data types varies by country. There is no information in Hungary available to estimate dose therefore this data source will not be included in analyses of dose.

The maximum lookback period for ascertaining characteristics before abrocitinib initiation will be 12 months (365 days), but will vary for a given RMM measure, per SmPC. Full country-specific algorithms for all study variables, including RMM-specific lookbacks will be specified in the SAP.

Table 1 summarizes the data available by country for analysis of patient co-morbidities, and prior and current medication use. Table 2 summarizes types of RMMs and specificity available by country for analysis. ANNEX 3. ADDITIONAL INFORMATION provides preliminary definitions of the codes to be used to define each element, per country.

Table 1. Availability of patient co-morbidities and concomitant medications in each country

	Denmark	France	Sweden	Spain 1	Hungary
Co-morbidities					
Acne	No	No	No	Yes	Yes
Allergic conjunctivitis	No	No	No	Yes	Yes

	Denmark	France	Sweden	Spain	Hungary
Allergic rhinitis	No	No	No	Yes	Yes
Anxiety	If treated in specialist care or through medication	No (unless hospitalized)	If treated in specialist care or through medication	Yes	Yes
Asthma	Identification of persisting asthma using hospital records and medication is possible.	Identification of persisting asthma using hospital records and medication is possible.	Yes	Yes	Yes

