RMM element	Denmark	France	Sweden	Spain ¹	Hungary ^{1, 2}
Pregnancy	Yes, completed pregnancies ending in live/still births in medical birth registry and terminations in the patient registry. Use of an algorithm to identify ongoing pregnancies may be applied pending further assessment	Yes, based on an algorithm using pregnancy outcomes (refer to Annex 3 for codes applied)	Yes, completed pregnancies ending in live/still births in medical birth registry	Yes	Yes, completed pregnancies ending in live/still births
Use of combined hormonal contraceptives or hormone replacement therapy	Yes, via dispensed prescriptions in Prescription registry	HRT is reimbursed. Very few hormonal contraceptives are reimbursed in France and are thus not identifiable in the SNDS.	Yes, via dispensed prescriptions in PDR	Partial. Some hormone contraceptive s are not reimbursed or are available over the counter.	Hormone replacement therapy data only
Major surgery	Yes, via procedure codes in NPR	Yes, via inpatient procedure codes	Yes, via procedure codes in NPR	Partial. Only if recorded as an ICD-10 procedure.	Yes
Inherited coagulation disorder (Factor V Leyden, Prothrombin gene mutation, Protein C deficiency, and Protein S deficiency)	Yes, to the extent identifiable via in/outpatient diagnoses	Yes, to the extent identifiable via inpatient diagnoses	Yes, to the extent identifiable via in/outpatient diagnoses	Yes if recorded in primary care	Yes
Live attenuated vaccines	Publicly-funded vaccine as recorded in the Danish Health Service Registry	Yes for reimbursed vaccines in high risk population (in	No	Yes	To be confirmed

Table 2. Availability of RMM elements for evaluation in each country

PFIZER CONFIDENTIAL

RMM element	Denmark	France	Sweden	Spain ¹	Hungary ^{1, 2}
	(10). Only the pathogen is recorded (e.g., MMR); however, it is possible to identify live vaccine based on what is used according to the Danish Health Authority. A small number of influenza vaccines from Patient Registry.	which it is reimbursed: pregnant women, patients with chronic diseases, patients 65 years or older) such as MMR, DT-Polio and BCG vaccines, not for Rotavirus, chicken Pox, Dengue, Yellow Fever.			
Severe hepatic impairment	Yes ⁵	Yes ⁵	Yes ⁵	To be confirmed ⁵	Yes ⁵
Diabetes	Yes, in/outpatient diagnoses	Yes, via inpatient diagnoses and Long term disease registration	Yes, via in/outpatient diagnoses	Yes if registered in primary care	Yes

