3) The proportion of patients with evidence of having risk factors and the number of risk factors for VTE, MACE, malignancy excluding NMSC, NMSC, and serious infection (including age 65 years or older, estimated dose of >100 mg/day for patients ages 65 or older, history of atherosclerotic disease, malignancy, pregnancy, history of VTE, use of combined hormonal contraceptives or hormone replacement therapy, major surgery, inherited coagulation disorder, diabetes, history of serious or opportunistic infection, TB) within 6 months prior to initiation of treatment with abrocitinib

4) The count and proportion of patients with evidence of having received live attenuated vaccines (e.g., measles, mumps, rubella) 4 weeks prior to and during treatment with abrocitinib

5) The count and proportion (among all pregnant women identifiable in a given database) of women in whom pregnancy overlaps with abrocitinib use

6) The count and proportion patients identified with severe hepatic impairment up to 6 months prior to or during treatment with abrocitinib

7) The count and proportion of patients aged <12 years on the index date

PFIZER CONFIDENTIAL

Abrocitinib B7451085 NON-INTERVENTIONAL STUDY PROTOCOL Version 2.0, 23 May 2024 8) The count of proportion of patients with an estimated starting dose > 100mg/day, and a description of the duration of use (median and IQR)

All proportions will be reported with 95% CIs.

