17. ANNEX 3. ADDITIONAL INFORMATION

Annex 3 Table A1: Preliminary variable definitions in each database (subject to refinement in the SAP)

Variable definitions for data from Spain (SIDIAP) and Hungary (NHIFA) will be included in the SAP.

RMM element	Denmark	France	Sweden
Complete blood count: absolute lymphocyte count, absolute neutrophil count, platelet count and haemoglobin level	Potential candidate example codes (subject to refinement): NPU codes NPU01960 B— Erythrocytes NPU02902 B— Neutrophilocytes; NPU02636 B— Lymphocytes; num.c. NPU02319 B— Haemoglobin(Fe); NPU02322 P— Haemoglobin(Fe); NPU027411 P— Haemoglobin NPU03568 B— Thrombocytes	Complete blood count including platelets: TNB code 1104	No
Lipid panel total cholesterol, HDL, LDL, and TG	Potential candidate example codes (subject to refinement) NPU codes total cholesterol: NPU01566, NPU18412 High-density lipoprotein: NPU01567, NPU10157, low-density lipoprotein: AAB00101-102, NPU01568, NPU10171, Triglycerides: NPU03620, NPU04094	TNB codes: total cholesterol: 0580, TG: 0590, c-LDL: 2001, exploration of lipid abnormality: 0996 (test only, no result)	No
Hepatitis B screening	No	TNB codes: Hepatitis B screening: 4500, screening IgM anti-HVC: 4501	No
Hepatitis C screening	No	TNB codes: Quantitative genome (RNA) detection: 4124, genotyping HVC: 4125	No
TB screening	No	TNB code: 0243 (test only, no result)	No

PFIZER CONFIDENTIAL

CT24-WI-GL02-RF02 3.0 Non-Interventional Study Protocol Template For Secondary Data Collection Study 20-May-2021 Page 46

RMM element	Denmark	France	Sweden
Risk factors for VTE, MACE, malignancy and serious infection:			
History of VTE	ICD-10 codes I26, I82.0, I82.2; I82.3, I82.8, I82.9	ICD-10 codes I26, I82.0, I82.2; I82.3, I82.8, I82.9	ICD-10 codes I26, I82.0, I82.2; I82.3, I82.8, I82.9
History of atherosclerotic disease	ICD I70.0 – I70.9	ICD10 code I70	ICD10 code I70
Malignancy	ICD-10 codes C00-C75, C81-C96	ICD-10 codes C00-C75, C81-C96; treatment proxy if relevant	ICD-10 codes C00-C75, C81-C96

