Pregnancy	ICD-10 codes O, Nomesco codes KMCA for Cesarean and/or linkage to the birth registry	ICD-10 codes: O80xx- O84xx (delivery), Z37xx (result of delivery), O01xx-O07xx (abortion and other abnormal products of conception) CCAM codes (medical acts) : (delivery) JQGD010, JQGD012, JQGD004, JQGD001, JQGD003, JQGD008, JQGD003, JQGD008, JQGD002, JQGD007, JQGA002, JQGD007, JQGA002, JQGA004, JQGA003, JQGA004, JQGA003, JQGA005 (termination) JNJD001, JNJD002, JNJP001 (ectopic pregnancy) JJFA001, JJFC00, JJJA002, JJJC002, JJLJ001, JJPA001, JJPC001, JQGA001 Outpatient healthcare code (PRS_NAT): (medical termination)	ICD-10 codes O + and/or linkage to the birth registry

RMM element	Denmark	France	Sweden
Use of combined hormonal contraceptives or hormone replacement therapy	ATC codes G03 Sex hormones and modulators of the genital system	ATC codes G03 Sex hormones and modulators of the genital system	ATC codes G03 Sex hormones and modulators of the genital system
Major surgery	NOMESCO Classification of Surgical Procedures candidate codes (https://sundhedsdatastyrelse n.dk/- /media/sds/filer/rammer-og- retningslinjer/klassisfikation er/bogudgave-klassifikaiton- operation.pdf?la=da) Operations on the nervous system: KA ; Operations on endocrine organs: KB ; Operations on the heart and large intrathoracic vessels: KF ; Operations on respiratory organs, chest, mediastinum and diaphragm: KG ; Breast surgeries: KH; Operations on digestive organs and spleen: KJ; Operations on the urinary tract, male genitalia and retroperitoneal tissue: KK; Operations on female genitalia: KL; Obstetric operations: KM; Operations on the musculoskeletal system: KN	CCAM codes for major surgery	Swedish KVÅ Selected procedure codes starting on N, J, L, G (further refinement to be done in the SAP)
Inherited coagulation disorder (Factor V Leyden, Prothrombin gene mutation, Protein C deficiency, and	ICD-10 D68.2 Hereditary deficiency of other clotting factors for Factor V Leyden, Prothrombin gene mutation, Protein C deficiency D68.8 Other specified coagulation defects for	ICD-10 D68.2 Hereditary deficiency of other clotting factors for Factor V Leyden, Prothrombin gene mutation, Protein C deficiency	ICD-10 D68.2 Hereditary deficiency of other clotting factors for Factor V Leyden, Prothrombin gene mutation, Protein C deficiency

RMM element	Denmark	France	Sweden

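### The preliminary code for combined contraceptive or HRT use is the whole of ATC group G03, which is wider than the named risk factor and, if kept, would over-count it

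*Protocol*

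**What the plan says.** Item 3 of Section 9.7.1 will report "The proportion of patients with evidence of having risk factors and the number of risk factors for VTE, MACE, malignancy excluding NMSC, NMSC, and serious" (the last group in that list being infections). One of the listed factors is "use of combined hormonal contraceptives or hormone replacement therapy". Table 2 in Section 9.3 names the same element and describes how far each country can capture it.

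Annex 3 Table A1 has a row labelled "Use of combined hormonal contraceptives or hormone replacement therapy". The cells for Denmark, France and Sweden carry the same definition: "ATC codes G03 Sex hormones and modulators of the genital system". No subgroup is picked out and no code outside G03 is added. Definitions for Spain and Hungary are left to the SAP.

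Two statements bear on the standing of this definition. Table A1 is headed "Preliminary variable definitions in each database (subject to refinement in the SAP". Section 9.3 adds: "Full country-specific algorithms for all study variables, including RMM-specific lookbacks will be specified in the SAP".

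On completeness, Table 2 says of France: "Very few hormonal contraceptives are reimbursed in France and are thus not identifiable in the SNDS". It describes Spain as partial and Hungary as having HRT data only. Section 9.9 also names oral contraceptives among the services that may be under-ascertained when only reimbursed items are recorded.

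**The concern.** The element is narrow: combined contraceptives, or HRT. The code is broad: every sex hormone and every genital-system modulator in one ATC group. Anyone dispensed any drug in that group within the lookback would be flagged, whether or not the drug belongs to the named risk factor.

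The study exists to show whether prescribers consider risk factors before starting abrocitinib. A proportion raised by unrelated drugs would suggest that more at-risk patients are being started than is the case. Because item 3 also reports how many risk factors each patient has, the same misclassification enters that count.

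The limitations in Section 9.9 prepare the reader for under-recording only. A reader who relies on them would take the reported figure as a lower bound, which it need not be.

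**Working it through.** **Inputs**

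- The element to be measured: Section 9.7.1 item 3, Table 2, and the Annex 3 row label. All three name the same element.
- The code: the whole of G03 in three countries (Annex 3 Table A1).
- The Protocol states no expected or observed use of this element, so there is no figure to reproduce.
- For scale only, the sample size in Section 9.5: 0.5 × 0.5 × 1.959964² / 0.05² = 384.15, rounded up to 385, as the Protocol states. This is a precision benchmark, not a forecast for any country.
- Three assumed quantities, none of them in the Protocol: t, the true share of patients using the named element; u, the share using only other G03 drugs; m, the share of true users that the code or database does not capture.

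**Step 1: code against label.** The group title printed in Annex 3 covers sex hormones and modulators generally. The row label covers two specific uses. No outside source is needed to see that the first is wider.

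**Step 2: direction.** Reported proportion = t(1 − m) + u, so the error is u − t·m. With full capture (m = 0) the error equals u, which cannot be negative. The broad code by itself can only add patients; a downward error needs missed true users.

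**Step 3: size with full capture (m = 0).** Each cell gives the reported proportion and, in brackets, the share of flagged patients who truly have the factor, t/(t + u).

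| True use t | u = 2% | u = 5% | u = 10% | 95% CI half-width at t, n = 385 |
|---|---|---|---|---|
| 5% | 7% (71%) | 10% (50%) | 15% (33%) | 2.2 points |
| 10% | 12% (83%) | 15% (67%) | 20% (50%) | 3.0 points |
| 20% | 22% (91%) | 25% (80%) | 30% (67%) | 4.0 points |

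The half-width is 1.959964 × √(t(1 − t)/385); for t = 10% this is 1.959964 × √(0.09/385) = 0.030. Over-capture of 2 points lies inside the sampling error in every row, and over-capture of 5 points lies outside it in every row.

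**Step 4: the risk-factor count.** Each patient flagged only through another G03 drug gains one factor, so the mean count rises by u, that is by 0.02 to 0.10 per patient under these assumptions. The proportion with at least one factor rises by at most u, and by less where such patients already have another factor.

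**Step 5: offset from missed users.** Taking t = 20%, u = 2% and m = 10%, the reported figure is 0.20 × 0.90 + 0.02 = 0.20, so the net error is zero. Even then only 0.18/0.20 = 90% of those flagged are true users. France is where this offset matters most, because Table 2 says most contraceptives cannot be seen there. The same code in France would measure HRT plus whatever other G03 drugs are reimbursed, which is not what it would measure in Denmark or Sweden.

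**The case against.** The strongest reply is that the Protocol does not fix this definition. The heading of Table A1 makes every row preliminary, Section 9.3 sends the full algorithms to the SAP, and narrowing an ATC group to subgroups is ordinary SAP work. The SAP is not available here. This stands, and it lowers the severity. It does not remove the point, because the complaint is about a code that is stated and does not match its label, not about a missing detail. Some other rows carry their own caution (the Danish laboratory codes are called candidate examples, and the Swedish surgery codes are marked for further work). The G03 row carries none and is identical in three countries, so it could easily be copied forward.

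A second reply is that the study is descriptive, this is one of about a dozen factors in one list, and no threshold or test depends on it. That also stands and limits the consequence.

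A reader might go further and infer that G03 also loses combined products coded elsewhere in the ATC system. The Protocol does not reproduce the ATC index and does not mention any such product, so this is something to check, not a finding. A reader might also apply a fixed inflation factor to all three countries. Any such factor is the reciprocal of an assumed share of G03 use, and Table 2 shows that the mix cannot be the same in France as in the Nordic countries.

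**Conclusion.** The point holds in a limited form. In Denmark, France and Sweden the stated preliminary definition is wider than the element it is meant to measure, and the Protocol does not disclose the over-capture that would follow. If it is kept, this component and the number of risk factors are overstated wherever true users are well captured. In France the direction of the net error is not established.

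The size cannot be derived from the Protocol. The range of 12% to 20% against a true 10% rests on assumed use of other G03 drugs alone by 2% to 10% of patients, and on no missed true users.

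The documents do not support saying that the reported proportion is already wrong, since the SAP may narrow the code. Nor do they support speaking of a distorted VTE proportion: item 3 gives a single list serving VTE, MACE, malignancy, NMSC and serious infection. The point does not extend to Spain or Hungary, whose definitions are not in Annex 3. Severity is minor to moderate.

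**What to change.** In Annex 3 and the SAP, replace G03 with two explicit lists of ATC subgroups, one for combined contraceptives and one for HRT, and state that the remaining G03 subgroups are excluded. Check both lists against the ATC index, including whether any combined product is coded outside G03.

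Report contraceptives and HRT separately where a country captures essentially only one of them. Table 2 indicates this for France, and for Hungary once its definition is written. Add a sentence to Section 9.9 on what the element measures in each country, so that the figures are not compared as if they were the same.

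The cost is one code-list edit and one extra line in the output tables. The check is best done before data applications are final: Section 9.7.1 notes that permissions and applications may need amending when variables are added, which would matter if a needed product turned out to lie outside G03.

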9.4. Data sources

This study will utilize secondary routinely collected data from population-based electronic registers in Denmark, Sweden and Spain, and a nationwide healthcare databases in France and Hungary. These secondary data sources were selected based on the expected required data elements' availability and projected sample size/number of patients with abrocitinib exposure during the study period. The data sources for this study are described below:

Denmark: Denmark's population-based registers, linkable by a unique identifier, the central person registration (CPR) number, assigned to all residents at birth or upon immigration) contain routinely collected data for the country's entire population of 5.8 million individuals (11, 12). The Danish National Prescription Registry contains information on all prescription medicines dispensed at Danish community pharmacies with prescriptions, including vaccinations, recorded via Anatomical Therapeutic Chemical (ATC) codes. Prescriptions administered at specialist hospital-based clinics are captured in the Danish National Patient Register, and tentatively from 2023, in the Danish Hospital Medicines Register (currently in development (13)). Newly approved drugs, especially expensive treatments, are often first prescribed or administered at the specialist hospital clinics with follow-up with general practitioners. Such treatments (active substance) may be identifiable via treatment codes in the Danish National Patient Register. The Danish National Patient Register records diagnoses (WHO International Classification of Diseases (ICD)-10 and ICD-11 codes) and procedures (Nordic Medico-Statistical Committee [NOMESCO] codes) during inpatient or outpatient hospital encounters. Danish Cancer Registry has mandatory reporting of primary malignancies since 1987. Danish Register of Laboratory Results collects information on hospitalperformed laboratory tests. Danish Medical Birth Registry will be used to identify pregnancies ending in a live or stillbirth (14-21).

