Protein S deficiency)	others including Protein S deficiency ICD-10 codes (Danish version) D685A Coagulation factor V Leyden mutation, bp 1691 (heterozygous) D685B Coagulation factor V Leyden mutation bp 1691 (homozygous) D685E Prothrombin, mutation bp 20210 (heterozygous) D685F Prothrombin, mutation bp 20210 (homozygous) D685K Protein C deficiency D685L Protein S deficiency	D68.8 Other specified coagulation defects for others including Protein S deficiency	D68.8 Other specified coagulation defects for others including Protein S deficiency
Live attenuated vaccines	Vaccine type as recorded in the Danish Health Service Registry The registry list the vaccine types, only pathogen e.g., MMR vaccine etc. However, it is possible to identify live vaccine based on what is used according to the Danish Health Authority. This registry records vaccines that are paid by public. Travel vaccines and vaccines paid by employer will not.	Yes for reimbursed vaccines such as MMR, DT-Polio and BCG vaccines, not for Rotavirus, chicken Pox, Dengue, Yellow Fever.	No
Diabetes	ICD-10 codes: E10-E14	ICD-10 codes: E10-E14	ICD-10 codes: E10- E14
Tuberculosis	ICD-10 codes: A15-A19	ICD-10 codes: A15-A19	ICD-10 codes: A15- A19
Serious and opportunistic infection	Serious infection: ICD-10 codes ¹ as primary diagnosis at a hospital contact with a minimum of 1 overnight stay A00-B99, D73.3, E06.0, E32.1, G00-G02, G04.2, G05-G07, H00.0, H44.0, H60.0-H60.3, H66-H67,	Refer to codes listed for Denmark	Refer to codes listed for Denmark

PFIZER CONFIDENTIAL

CT24-WI-GL02-RF02 3.0 Non-Interventional Study Protocol Template For Secondary Data Collection Study 20-May-2021

RMM element	Denmark	France	Sweden
	H70, I30.1, I40.0, J00-J22,		
	J32, J34.0, J36, J38.3, J39.0-		
	J39.1, J44.0, J85, J86, K04.4,		
	K04.6, K04.7, K10.2, K11.3,		
	K12.2, K14.0, K57.0, K57.2,		
	K57.4, K57.8, K61, K63.0,		
	K65, K65.1, K65.2, K65.9,		
	L00-L08, L30.3, M00-M01,		
	M46.2-M46.5, M60.0,		
	M65.0, M71.0, M71.1,		
	M72.6, M86, N10, N11,		
	N12, N13.6, N15.1, N15.9,		
	N30.0 N30.8, N34.0, N41.2,		
	N43.1, N45.2, N45.3, N45.4, N48.2, N61, N70, N73, or		
	N75.1, U071,		
	Denmark only: Z861A (the		
	code list will be refined in		
	the SAP to map ICD-10-CM		
	codes to ICD-10 equivalents		
	whenever feasible)		
	Opportunistic infection:		
	ICD-10 codes† A02.1,		
	A02.21, A02.22, A02.23,		
	A02.24, A02.29, A07.2,		
	A07.3, A18.7, A18.59,		
	A18.4, A19.0- A19.9, A18.6,		
	A18.15, A18.4, A18, A17.0,		
	A18.89, A15.0, A18.11,		

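### The Danish live-vaccine indicator leaves out the National Prescription Registry, although Sections 9.3 and 9.4 say vaccinations are identified by ATC code and that this registry holds them

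*Protocol*

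**What the plan says.** Four places in the protocol bear on how live vaccines are found in Denmark.

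- **Section 9.3, text.** The general rule is "Abrocitinib and concomitant medications and vaccinations will be identified using ATC codes".
- **Section 9.4, Denmark.** The National Prescription Registry is described as covering prescription medicines "dispensed at Danish community pharmacies with prescriptions, including vaccinations, recorded via Anatomical Therapeutic Chemical (ATC) codes". No condition about public payment is attached.
- **Section 9.3, Table 2, live attenuated vaccines.** The Danish cell names a different source: "Publicly-funded vaccine as recorded in the Danish Health Service Registry". It notes "Only the pathogen is recorded (e.g., MMR" and so on, says live products can be inferred from what the Danish Health Authority has in use, and adds "A small number of influenza vaccines from Patient Registry".
- **Annex 3, Table A1.** The Danish entry is "Vaccine type as recorded in the Danish Health Service Registry", with the coverage statement "This registry records vaccines that are paid by public. Travel vaccines and vaccines paid by employer will not".

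The indicator itself is item 4 of Section 9.7.1: the count and proportion of patients with evidence of a live attenuated vaccine in the 4 weeks before abrocitinib or during treatment. Section 9.9 says vaccinations may be under-recorded in Denmark and France, and puts the incompleteness down to reimbursement-based recording.

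**The concern.** The general text and the Danish variable definition point to different sources. The source that the definition names is limited to publicly paid vaccines and carries no product code. The source that it does not name is described in the same protocol as holding vaccinations by product code, with no payment restriction.

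Avoidance of live vaccines is one of the eight objectives in Section 8.2, and Denmark matters to it. By Table 2, Sweden has no vaccine data, France has only certain reimbursed vaccines in high-risk groups, and Hungary is unconfirmed. The indicator counts events that should not happen, so every missed record lowers the reported proportion and makes prescribing look more adherent. The indication covers adults and, since March 2024, adolescents. Travel vaccines, which Annex 3 says are not captured, could well be relevant in that population, though the protocol gives no data on this.

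**Working it through.** No figure in the protocol bears on this point, so there is nothing to reproduce. The check is a comparison of passages, followed by the direction of the error.

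**Step 1. Coverage of each Danish source, as the protocol describes it.**

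| Source | Where described | Vaccines held | Coding | Named for the live-vaccine indicator? |
|---|---|---|---|---|
| Health Service Registry | Table 2, Annex 3 | Publicly paid; not travel or employer-paid | Pathogen | Yes |
| Patient Registry | Table 2 | A few influenza vaccines | Not stated | Yes, in Table 2 only |
| National Prescription Registry | Section 9.4 | Dispensed on prescription at community pharmacies | ATC | No |

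**Step 2. Is the third source already in the study?** Yes. The Danish cell of Table 2 for hormonal contraceptives and hormone replacement therapy names it.

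**Step 3. Which records are affected?** Those for live vaccines that were (a) dispensed on prescription at a community pharmacy, (b) not publicly paid, and (c) within the 4 weeks before or during treatment. On the protocol's own description they are in the Prescription Registry and absent from the Health Service Registry. The few influenza vaccines from the Patient Registry do not cover travel vaccines.

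**Step 4. Direction.** Let t be the true proportion with a live vaccine, m the share of these vaccinations outside the sources named, and f the share of those that the Prescription Registry would recover.

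- Reported as written: t × (1 − m), which is never above t.
- Reported with the Prescription Registry added: t × (1 − m + m × f), which is never below the figure as written and never above t.
- Gain: t × m × f.

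**Step 5. Illustration with assumed values.** The protocol gives none of t, m or f. Take t = 2%:

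| m (assumed) | Reported as written | Gain from the fix, f from 0 to 1 |
|---|---|---|
| 10% | 2% × 0.9 = 1.8% | 0 to 0.2 points |
| 30% | 2% × 0.7 = 1.4% | 0 to 0.6 points |
| 50% | 2% × 0.5 = 1.0% | 0 to 1.0 points |
| 80% | 2% × 0.2 = 0.4% | 0 to 1.6 points |

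The table shows only that the sign is fixed and the size is open. If hardly any live vaccines are dispensed through community pharmacies, f is near 0 and the fix gains almost nothing.

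**The case against.** The strongest reply is that nothing has been fixed yet. Annex 3 is headed as preliminary and open to refinement in the SAP, Section 9.3 leaves full country-specific algorithms to the SAP, and Table 2 is an availability table rather than a scoring rule. Sections 9.3 and 9.4 together already permit an ATC search, so on this view only the wording needs aligning. Section 9.9 also names Denmark as under-recorded and warns that a missing record does not show that no vaccine was given.

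Part of this stands. A reader might infer that the protocol forbids use of the Prescription Registry for vaccines. It does not say so; it only fails to name it. A reader might also infer that Denmark will report near-perfect adherence. The protocol gives no expected result, and Section 9.9 cautions against that interpretation.

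The reply does not remove the point:

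- The protocol does state a source for Denmark, and that statement disagrees with its own general text. This is not detail left for later.
- The Table 2 footnote that leaves availability to be confirmed in the SAP covers Spain and Hungary, not Denmark.
- Section 9.7.1 limits analysis to the data available in each country and refers to Tables 1 and 2 for this.
- Section 9.9 treats the gap as a consequence of reimbursement-based recording, whereas Section 9.4 describes a Danish source without that limit. A disclosed limitation does not recover records that another study source could supply.

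The reply is also right that live status can be inferred from pathogen and national use. ATC codes would be more direct, but this is a secondary benefit.

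**Conclusion.** The inconsistency is real and should be corrected. The Danish definition in Table 2 and Annex 3 does not follow the ATC rule in Section 9.3 and omits a registry that Section 9.4 says holds vaccinations. The resulting error can only lower the proportion with a live vaccine, and so can only favour apparent adherence.

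Its size is unknown. It is tempting to multiply a guessed self-paid share by a guessed pharmacy share and report a percentage of events missed. The documents support neither input, so no such percentage is offered. The conclusion rests on one assumption: that at least some live vaccines given to Danish users are dispensed on prescription at community pharmacies without public payment. Section 9.4 makes this possible but does not quantify it. Vaccines given from clinic stock or supplied by an employer may be missed even after the correction, so the indicator would remain a lower bound.

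**What to change.** 1. In Table 2 and Annex 3, define the Danish indicator as a Health Service Registry or Patient Registry record, **or** a Prescription Registry dispensing of a listed live-vaccine ATC code, in the window already set in Section 9.7.1 (4 weeks before and during treatment). If the Prescription Registry cannot be used for vaccines, say why and correct Sections 9.3 and 9.4 instead.
2. Include the live-vaccine ATC codes in the Danish data application.
3. Revise Section 9.9 so that the Danish limitation describes what remains uncaptured after this source is added, rather than attributing all of it to reimbursement.

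The cost is a short code list applied to a registry that the study already uses. It should not be assumed that the records are already in hand: the protocol is dated 23 May 2024 and data collection is planned to start on 31 December 2024. Section 9.7.1 also warns that permissions and applications may need amending for added variables, so the codes are best settled before the request is made. The drawback is modest: a dispensing date may precede administration, and some dispensed vaccines may never be given. Reporting the count by source would let readers see how much of the Danish figure rests on dispensings.
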